Visit 1: Baseline information will be collected including History and Physical Examination, EKG, routine clinical blood work. Women will give a urine sample for a pregnancy test. Patients will fill out baseline questionnaires including the Patient Assessment of GI Symptoms (PAGI-SYM) for assessment of GI symptoms over the past 2 weeks. Inclusion and Exclusion criteria will be reviewed to determine if the patient is eligible for the study. Patients meeting the inclusion criteria will be asked to participate and sign informed consent. Patients will be shown how to apply Sancuso patch using a placebo-containing patch. This will be worn by the patients for one week. Patients will be given a notebook containing the GCSI-DD sheets and fill out the GCSI-DD as baseline for one week and not take any 5-HT3 receptor antagonist during this time. A follow up appointment in one week will be scheduled.

Visit 2: Patients will return after the one week baseline period. The daily symptom questionnaires will be collected. Patients will fill out baseline questionnaires including the Patient Assessment of GI Symptoms (PAGI-SYM) for assessment of GI symptoms over the past 2 weeks, SF-36 to assess their quality of life, HAD questionnaire to assess for symptoms of anxiety and depression, and a modified McGill Pain inventory to assess for abdominal pain. Patients will be given Sancuso® for one week. The placebo patch will be removed and the active Sancuso will be applied at the visit to ensure that it sticks. Patients will continue to fill out the GCSI-DD on a daily basis and not take any 5-HT3 receptor antagonist. A follow up appointment in one week will be scheduled.

Visit 3: Patients will be seen after one week of treatment. The GCSI daily diaries will be collected. The therapeutic response of the patients will be enquired using the simple Clinical Patient Grading Assessment Scale (CPGAS). Patient will be asked if any adverse or side effects occurred while being treated with Sancuso. Patient will then fill out a symptom side effect questionnaire that also asks about difficulty with wearing the patch. The old Sancuso patch will be removed and a new Sancuso® patch will be applied for another one week. A follow up appointment in one week will be scheduled.

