Visit 4: Patients will be seen after the second one week of treatment. The GCSI daily diaries will be collected. The therapeutic response of the patients will be enquired using the simple Clinical Patient Grading Assessment Scale (CPGAS). Patients will fill out the Patient Assessment of GI Symptoms (PAGI-SYM), SF-36, HAD questionnaire, a modified McGill Pain

inventory, and a symptom side effect questionnaire. Patients will stop treatment with Sancuso® at this time, and be followed for an additional week of treatment off medication. Patients will continue to fill out the GCSI-DD on a daily basis and not take any 5-HT3 receptor antagonist. A follow up appointment in one week will be scheduled.

Visit 5: Patients will be seen after one week after cessation of treatment. The GCSI daily diaries will be collected. Patients will fill out the symptom side effect questionnaire. After this visit, the study period is over and the patient returns to clinical care.

f) Study Endpoints

Primary and Secondary Endpoints:

Primary:	Nausea and Vomiting severity scores using the GCSI-DD
Secondary:	Total Gastrointestinal Cardinal Symptom Index
-	Clinical Patient Grading Assessment Scale (CPGAS)

Patients will fill out daily information of their symptoms of gastroparesis using the Gastroparesis Cardinal Symptom Index Daily Diary (GCSI-DD). The Gastroparesis Cardinal Symptom Index (GCSI) is a validated patient-reported outcome for gastroparesis daily recording of symptoms. Several symptoms of gastroparesis including nausea, vomiting, retching, stomach fullness, unable to finish a meal, feeling excessively full after meals, bloating, belly visibly larger will be monitored. This is used in clinical practice and will be performed in this project.

For this study, the therapeutic response of the patients will also be enquired using the simple Clinical Patient Grading Assessment Scale (CPGAS). Patients will be asked if they improved, stayed the same, or worsened with Sancuso® treatment. The clinical response of their gastroparesis symptoms to Sancuso treatment with gradations from (+7) = completely better; (0) = no change, and (-7) = very considerably worse. Responders are defined as those with score of >0 and non-responders with score of \leq 0 by CPGAS. Patients will be asked if they experienced any side effects with Sancuso® treatment and to describe any side effects. Other than your GI symptoms, how have you been feeling?

Adverse events will be recorded.

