Risks of the Study: For the open label study, data is being recorded about their medical condition. All data will be kept confidential. Data will be entered into an Excel spreadsheet in a password protected computer accessible only be the study coordinator and the PI.

Risks of Sancuso®:

The decision to enroll a patient in this study with Sancuso® will be made after discussing all available treatment options with the patient. The following risks of Sancuso® might occur. The most common adverse reaction with Sancuso® is constipation. The patch may also cause some local skin irritation. In clinical trials with Sancuso®, application site reactions were reported which were generally mild in intensity and did not lead to discontinuation of use. The incidence of reactions was comparable with placebo. If severe reactions, or a generalized skin reaction occur (e.g. allergic rash, including erythematous, macular, papular rash or pruritus) the patch must be removed. Granisetron may be affected by direct natural or artificial sunlight. Patients must be advised to cover the patch application site, e.g. with clothing, if there is a risk of exposure to sunlight throughout the period of wear and for 10 days following its removal because of a potential skin reaction.

The safety of Sancuso® was evaluated in a total of 404 patients undergoing chemotherapy who participated in two double-blind, comparator studies with patch treatment durations of up to 7 days. The control groups included a total of 406 patients who received a daily dose of 2 mg oral granisetron, for 1 to 5 days. Adverse reactions considered by the investigators as drug-related occurred in 8.7% (35/404) of patients receiving Sancuso® and 7.1% (29/406) of patients receiving oral granisetron. The most common adverse reaction was constipation that occurred in 5.4% of patients in the Sancuso® group and 3.0% of patients in the oral granisetron group. Table 1 lists the treatment emergent adverse reactions that occurred in at least 3% of patients treated with Sancuso® or oral granisetron.

Table 1: Incidence of Adverse Reactions in Double-Blind, Active Comparator Controlled Studies in Cancer Patients Receiving Chemotherapy (Events ≥ 3% in either group)

Body System Preferred Term	Sancuso® TDS N=404 (%)	Oral granisetron N=406 (%)	
Gastrointestinal disorders			
Constipation	5.4	3.0	
Nervous system disorders			
Headache	0.7	3.0	

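### The open question in section 10(f) can be read as leaving out constipation, the patch's most common named adverse reaction; rewording it and securing one direct constipation item would close the gap cheaply

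*Combined protocol and SAP*

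**What the plan says.** Section 10(f) of the protocol describes the patient's global rating of change (CPGAS) and then two questions about how the patient has been. The first is about side effects: "Patients will be asked if they experienced any side effects with Sancuso® treatment and to describe any side effects". The second is open and carries an exclusion: "Other than your GI symptoms, how have you been feeling". The section closes by stating that adverse events are recorded. Neither question is tied to a particular visit.

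The visit schedule in 10(e) adds other enquiries. At Visit 3: "Patient will be asked if any adverse or side effects occurred while being treated with Sancuso", followed by a written form, "Patient will then fill out a symptom side effect questionnaire that also asks about difficulty with wearing the patch". The same form returns at Visit 4 ("inventory, and a symptom side effect questionnaire") and at Visit 5 ("Patients will fill out the symptom side effect questionnaire"). Section 10(g) also lists it among the forms for the study visits. Its items are not in the text available for review, where the appendices appear by title only.

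On known harms, section 11 reports: "The most common adverse reaction was constipation that occurred in 5.4% of patients" on the patch, against 3.0% on oral granisetron. Table 1 places constipation under gastrointestinal disorders.

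The diary symptoms named in 10(f) are: "nausea, vomiting, retching, stomach fullness, unable to finish a meal, feeling excessively full after meals, bloating, belly visibly larger will be monitored". Constipation is not on that list, nor among the nine GCSI symptoms in section 6.

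**The concern.** A general question about how the patient has felt does a job that a side-effect question cannot: it does not require the patient to decide what caused the symptom. That matters here because the patients have a chronic GI disorder and may put constipation down to their disease. In this protocol the one question free of attribution is also the one that sets GI symptoms aside, and the leading known reaction to the patch is a GI event. The diary does not pick it up either, on the symptoms listed.

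At stake is the safety description. The opening summary says that safety information will be collected and that a larger double-blind study would follow encouraging results. With 30 patients, very few cases of any one reaction are expected, so one unrecorded case would noticeably change the tolerability picture.

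**Working it through.** The plan gives no figure for this point, so there is nothing to reproduce. The check sets the collection routes side by side and then gives a scale.

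**Step 1. Is constipation the leading named harm, and a GI event?** Table 1 in section 11 lists two events that reached 3% in either group: constipation (5.4% patch, 3.0% oral) and headache (0.7% patch, 3.0% oral). Constipation is the only one at or above 3% on the patch. It is classed as gastrointestinal.

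**Step 2. Which routes could record it?**

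| Route | Place | Excludes GI symptoms? | Patient must attribute to the patch? |
|---|---|---|---|
| Side-effect question | 10(f), no visit given | No | Yes, as worded |
| Open question | 10(f), no visit given | Yes, if read literally | No |
| Spoken enquiry | 10(e), Visit 3 only | No | Less so: it adds adverse effects and refers to the time on treatment |
| Side-effect questionnaire | 10(e), Visits 3, 4, 5; also 10(g) | Unknown, items not shown | Unknown |
| Daily diary | 10(f) | Constipation not among listed symptoms | No |

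The serious-event reporting text in 10(g) does not help with ordinary constipation. The text does not say whether a new or worsened GI symptom counts as a non-serious adverse event.

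**Step 3. Scale.** Inputs: n = 30 (sections 10(c) and 10(d)) and p = 0.054 (section 11). That rate comes from chemotherapy patients wearing the patch for up to 7 days; this trial treats for two 7-day patches. Carrying it over is an assumption.

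- Expected cases: 30 × 0.054 = 1.62.
- Chance of at least one case: 1 − (1 − 0.054)^30 = 1 − 0.946^30 = 81.1%.

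Let s be the share of cases that gets recorded. The documents give no value for s, so this is a range and not an estimate. Expected recorded cases are 30 × 0.054 × s, and the chance of recording at least one is 1 − (1 − 0.054s)^30.

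| s (assumed) | Apparent rate | Expected recorded cases | Chance of recording at least one |
|---|---|---|---|
| 100% | 5.4% | 1.62 | 81.1% |
| 75% | 4.05% | 1.22 | 71.1% |
| 50% | 2.7% | 0.81 | 56.0% |
| 25% | 1.35% | 0.41 | 33.5% |

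At s = 0 nothing would be recorded, but the unrestricted routes in Step 2 mean that the documents do not support that case.

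**The case against.** A reader might infer that patients are told to leave out GI events and that constipation will therefore be under-counted. The documents do not support that, for four reasons.

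- The open question is not the only adverse-event enquiry. The question just before it has no GI exclusion, and neither does the Visit 3 enquiry. The latter refers to the treatment period and names adverse effects as well as side effects, so it depends less on the patient's view of cause.
- The side-effect questionnaire may ask about constipation by name. If it does, most of the gap closes. That its items cannot be seen is no evidence that the item is missing.
- The question follows directly on the CPGAS rating of gastroparesis symptoms. Its reference to the patient's GI symptoms can naturally mean the symptoms just rated, with everything else, constipation included, still invited.
- The capture shares above are assumptions. Even at half capture the difference is 1.62 − 0.81 = 0.81 of a patient, in an uncontrolled study with no safety endpoint.

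Two wider inferences should also be set aside. Worsening of gastroparesis symptoms is not lost, because the diary records the listed symptoms daily and the CPGAS runs down to −7. Nor do the documents give any basis for saying that unrecorded constipation would distort the total GCSI score.

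What remains is narrower. The wording has two readings, and under one of them the only attribution-free question leaves out the leading known reaction. The spoken Visit 3 enquiry is not listed at Visits 4 or 5, although the second treatment week goes beyond the exposure behind the 5.4%.

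**Conclusion.** The point holds as a risk in the wording, worth correcting because correction is nearly free. It is not a demonstrated error. Constipation may be missed in reply to this one question, particularly when the patient does not attribute it to the patch. Whether the study as a whole would miss it turns on the unseen questionnaire and on how patients hear the question.

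The size of any under-count cannot be derived from the documents. The one anchored figure is about 1.6 expected cases in 30 patients, and it rests on a rate from chemotherapy patients with up to 7 days of exposure carrying over to gastroparesis patients treated for 14.

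**What to change.** 1. In 10(f), remove the GI exclusion from the open question. Possible wording: *How have you been feeling since the last visit, including any new or worse stomach or bowel symptoms?*
2. State in the protocol that new or worsened GI events, including constipation, are recorded as adverse events whether or not the patient attributes them to the patch.
3. Confirm whether the side-effect questionnaire already has a direct constipation item. If not, add one. Ask it at Visits 2 to 5, with the Visit 2 answer as the pre-treatment baseline. The schedule in 10(e) does not list the questionnaire at Visit 2, so the baseline answer needs to be written in there.

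The cost is one reworded question, one clarifying sentence and at most one extra item at each of four visits already scheduled. Reported adverse-event rates will be slightly higher, and the Visit 2 answer helps to separate pre-existing constipation from new cases.

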The aim of this study is to determine the efficacy of Sancuso® (granisetron transdermal system) 3.1 mg/24 hours in improving symptoms of nausea and vomiting in patients with gastroparesis. This will be a prospective open-label study using Sancuso® to treat symptoms of nausea and/or vomiting in patients diagnosed with gastroparesis. Symptomatic patients with diabetic or idiopathic gastroparesis with nausea and/or vomiting will be enrolled. The Gastroparesis Cardinal Symptom Index Daily Diary (GCSI-DD) will be used to capture the severity of symptoms, including nausea and vomiting, at baseline for one week. Patients will then be treated with Sancuso[®]. Patients will continue to fill out the GCSI-DD on a daily basis while undergoing treatment with Sancuso® for two weeks. To determine if Sancuso® treatment helps improve symptoms of nausea and vomiting, the symptoms at baseline will be compared to symptoms after the first week and the second week of treatment. Thirty patients diagnosed with gastroparesis (approximately 15 with diabetic and 15 with idiopathic gastroparesis) will be treated on an open label basis with Sancuso®. The goal of this study is to demonstrate the efficacy of Sancuso® in treating nausea and/or vomiting in gastroparesis patients. Safety information will also be collected regarding any adverse effects. If the results are encouraging, as we expect them to be based on personal experience, a larger double blind study would be appropriate.

2) Protocol Title

Sancuso® in patients with nausea and/or vomiting from gastroparesis: An open label study.

3) IRB Review History

No prior IRB submission

4) Investigator

[name]; Temple University Hospital; GI Section; [name]; [contact]; Email: [contact]

5) Objectives

The aim of this study is determine the efficacy of Sancuso® in improving symptoms of nausea and vomiting in patients with gastroparesis.

The specific objectives of this study are to determine:

1) Determine the treatment response of Sancuso® in gastroparetic patients with nausea and/or vomiting.

2) Determine which specific symptoms of gastroparesis improve – nausea, vomiting, early satiety, abdominal distension, abdominal pain

3) To determine symptomatic responses in both diabetic and idiopathic gastroparesis

4) To determine the time course of symptom improvement (with Sancuso® for symptoms of gastroparesis;

The hypotheses to be tested include:

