The Principal Investigator will be responsible for the reporting and submission of serious (expected or unexpected) adverse events that occur during the conduct of this study to FDA on a MedWatch 3500a form. Additionally, the Principal Investigator will be responsible for providing the required study update reports to the Institutional Review Board (IRB). The Principal Investigator will also provide ProStrakan with a copy of the MedWatch 3500a completed for all serious adverse event reports. The information includes the investigator's assessment of causality. This information will be sent to the company within 10 days of receipt of the adverse event report by the Investigator. A copy of the completed MedWatch 3500a form submitted to FDA will be sent to [contact]. The company will enter all safety information in the Global Safety Database along with the investigator's assessment of relationship of the event to the study medication. Any follow up information will also be sent to the company within 10 days of receipt of the adverse of the adverse of the study medication. Any follow up information will also be sent to the company within 10 days of receipt of the information by the Investigator on a completed MedWatch 3500a form.

h) Data and Specimen Banking

Data will be stored on encrypted password-protected computer using a Microsoft Excel data base. No specimens will be obtained.

i) Data Management

Data will be entered into an Excel spreadsheet in an encrypted password protected computer accessible only to the study coordinator and the PI.

Descriptive analysis of the outcome variables will be constructed using Excel and SPSS.

Outcome measures

The primary outcome measures in this study are the GCSI-DD nausea/vomiting symptom scores. The secondary outcome measures are Total Gastrointestinal Cardinal Symptom Index and Clinical Patient Grading Assessment Scale (CPGAS). The percent of patients treated with Sancuso® that have improved symptoms of nausea, vomiting will be calculated both as a positive score on the CPGAS as well as a 25% improvement in the nausea score compared to baseline.

Data Analysis

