Descriptive analysis of the outcome variables will be constructed. Statistical analysis will be performed using SPSS. This study is designed to test the hypothesis that Sancuso® treatment provides improvement of gastroparetic symptoms. We will compare the absolute GCSI symptom scores before and after treatment using ANOVA for repeated measures. The symptom score improvement will be tested between the two treatment groups (diabetic and idiopathic gastroparesis) using ANOVA for repeated measures on ranks. Linear regression will be used to identify potential predictors of a beneficial symptomatic response to treatment.

Sample Size Determination

In a gastroparesis study at our institution with similar inclusion criteria, the average GCSI of 16 patients was 34.8 with standard deviation of 4.6. In a previous study at our institution, the absolute magnitude of symptom improvement for open label botulinum toxin was 38% (Miller 2002). The sample size in this study is calculated to show a benefit of Sancuso® by at least 30% reduction in the GCSI score. Assuming a standard deviation of 5 in the GCSI reduction of symptoms and with an α = .05 and β = .80, fifteen patients will be needed. We will recruit 15 diabetic patients and 15 idiopathic patients to enter this study to give adequate power to address the primary outcome variable - symptom response.

j) Confidentiality

Private health information (PHI) as defined by HIPAA will be collected as part of the research. These include: name, birthdate, telephone number, medical record number. All data will be kept confidential. Data will be entered into an Excel spreadsheet in an encrypted password protected computer accessible only be the study coordinator and the PI. The data will be deidentified.

k) Provisions to Monitor the Data to Ensure the Safety of subjects

This study involves minimal risk to the subjects. Patients will be monitored during the study in weekly study visits. The Sancuso® patch is being used to try to help reduce their symptoms of nausea and/or vomiting. The study is to allow recording of the response to treatment. All data will be kept confidential. Data will be entered into an Excel spreadsheet in an encrypted password protected computer accessible only be the study coordinator and the PI.

I) Withdrawal of Subjects

Patients have the option to not participate. Patients may elect at any time to stop treatment with Sancuso®.

11) Risks to Subjects

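### No rule for patients without a week-2 score: a repeated-measures ANOVA run in the ordinary way would drop them and modestly overstate improvement if poor responders stop the diary

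*Combined protocol and SAP*

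**What the plan says.** The primary outcome is given in section 10(i), Outcome measures: "The primary outcome measures in this study are the GCSI-DD nausea/vomiting symptom scores". The analysis follows under Data Analysis: "We will compare the absolute GCSI symptom scores before and after treatment using ANOVA for repeated measures". SPSS is named as the software, but no procedure within it. The time points come from the study summary: "the symptoms at baseline will be compared to symptoms after the first week and the second week of treatment".

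The diabetic/idiopathic comparison uses a related method: "The symptom score improvement will be tested between the two treatment groups (diabetic and idiopathic gastroparesis) using ANOVA for repeated measures on ranks". The responder measure is introduced with "The percent of patients treated with Sancuso® that have improved symptoms of nausea, vomiting will be calculated", either as a positive CPGAS score or as a 25% improvement in nausea.

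Diaries are handed in weekly. At Visit 3 (section 10(e)): "Patients will be seen after one week of treatment. The GCSI daily diaries will be collected". They do not depend on wearing the active patch, because they also run in the baseline week and after Visit 4: "Patients will stop treatment with Sancuso® at this time, and be followed for an additional week of treatment off medication".

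On withdrawal, section 10(l) says only that participation is optional and that "Patients may elect at any time to stop treatment with Sancuso". Nothing says whether the diary continues after early stopping, which patients enter the ANOVA, what is done about a missing weekly score, or how many diary days make one. No dropout rate is given.

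**The concern.** A classical repeated-measures ANOVA needs every level for every patient. With baseline, week 1 and week 2 as levels, a patient who hands in two weeks of diaries and then stops contributes nothing, although those two weeks are in hand. The rank version used to compare etiologies has the same property, with only about 15 patients per group.

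Whether this biases the result depends on who is lost. Section 10(b) enrols patients with at least moderate symptoms that conventional antiemetics have not controlled, and bars ondansetron and oral granisetron during the study. A patient not helped in week 1 has a reason to leave. That this would also end the diary is an inference; the plan does not say so. If it happens, the remaining patients look better than the treated group.

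At stake are the size of the reported effect, the time-course objective (which uses week 1) and the effect size carried into the larger double-blind study that the summary foresees.

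**Working it through.** **Inputs from the plan** (section 10(i), Sample Size Determination): mean GCSI 34.8, SD 4.6, target reduction 30%, SD of change 5, n = 30.

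**Assumptions, because the documents give no figure:** dropout 10% to 20%; correlation ρ between week-1 and week-2 change 0.5 to 0.7; gradual dropout on a logistic curve with slope 1 per SD of change, rising with poor response. All points are on the GCSI total, since no SD is given for the nausea/vomiting score.

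**Planned effect.** 0.30 × 34.8 = 10.44 points. (The stated 15 patients does not follow from 10.44 and SD 5: a paired t-test reaches power 0.93 at n = 5. That is a separate matter, and nothing here depends on it.)

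**Size of the bias.** If dropout depends on the change in one week, completers are too favourable in that week by some amount B, and in the other week by ρ × B.

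- Gradual 20% dropout: B = 0.87 points, so the other week is 0.5 × 0.87 = 0.44 to 0.7 × 0.87 = 0.61.
- Gradual 10% dropout: B = 0.46, other week 0.23 to 0.32.
- Upper bound, exactly the worst fifth by week-1 change leave: B = 5 × φ(−0.842)/0.8 = 5 × 0.280/0.8 = 1.75, so week 2 is 0.87 to 1.22.

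| 20% gradual dropout driven by | Overstated at week 1 | Overstated at week 2 | Left at week 2 if all observed weeks are used |
|---|---|---|---|
| week-1 change | 0.9 | 0.4–0.6 | about 0 |
| week-2 change | 0.4–0.6 | 0.9 | 0.5–0.7 |
| nothing related to response | 0 | 0 | 0 |

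The last column is a likelihood-type estimate that keeps the early data of those who leave. In the first row, using every patient's week-1 diary also removes the week-1 bias.

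**At the planned effect.** With 20% gradual week-1-driven dropout the completers' week-2 estimate is 10.86 to 11.06 against 10.44, an excess of 4% to 6%. If exactly the worst fifth leave, it is at most 11.6. Every one of 3,000 simulated trials per setting was significant.

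**With no true change** (6,000 simulated trials of 30 per setting, nominal 5%; 1,500 for the mixed model). With 20% gradual week-1-driven dropout, the three-level F-test with Greenhouse-Geisser correction is significant in 9% to 11% of trials, a paired baseline-to-week-2 test in 6% to 9%, and a mixed model in 5% to 6%. With 10% dropout the F-test gives 6%. If dropout follows the week-2 change, the F-test gives 10% to 12% and the mixed model 8% to 10%.

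**Group comparison.** If gradual dropout were 30% in one etiology and 10% in the other, with no true difference, completers would show a false week-2 difference of 0.40 to 0.57 points (raw scores; the plan uses ranks).

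**Why 5 points does not transfer to the primary score.** 34.8 over nine symptoms is about 3.9 per symptom, or 11.6 for three symptoms if all score alike. Five points would be 5/11.6 = 43% of that three-symptom sum.

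**The case against.** Several points on the other side stand.

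- The plan does not prescribe a completers-only analysis. A reader might infer that it does, but no SPSS procedure is named and the text says only before and after treatment. The summary can also be read as two separate comparisons with baseline. The week-1 diaries would then be kept, and at 20% gradual dropout only the paired-test rate of 6% to 9% would apply.
- The responder percentages are expressed among treated patients, which arguably sets their denominator already. What is missing there is how a treated patient without an assessment is counted.
- Loss may be small: treatment lasts two weeks, with weekly visits and a payment for each.
- The raised false-positive rates need a true mean change near zero. The plan itself cites a 38% improvement in an earlier open-label study of another treatment, so a change near zero is not what it expects.
- It is tempting to say that the bias is always worse at week 1, because those data are in hand. That holds only if dropout follows the week-1 change; it reverses if dropout follows the week-2 change.
- The mixed model is not a cure. If dropout depends on the unseen week-2 score, most or about half of the bias remains. At correlation 0.5 its F-test is then no better than the ANOVA's (10.4% against 9.9%).

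None of this supplies the missing rule. It limits the point to a modest, conditional bias that is cheap to reduce.

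**Conclusion.** The gap is real, and closing it is a cheap improvement. The plan names a method that ordinarily discards incomplete patients and says nothing about them. If poor responders stop the diary, with 20% gradual dropout, SD of change 5 and correlation 0.5 to 0.7, improvement on the GCSI total is overstated by about 0.4 to 0.6 points in one treatment week and 0.9 in the other; which week is worse depends on what drives dropout. Dropout rate, pattern and correlation are all assumptions, and the size on the primary nausea/vomiting score cannot be computed from the documents.

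A reader might infer that a positive result would be an artefact of missing diaries. The documents do not support that: at the planned 10.4-point effect significance does not change, and loss unrelated to response gives no bias. The false-positive rate rises only if the true change is near zero.

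**What to change.** In section 10(i), replace the ANOVA with a linear mixed model (MIXED in SPSS) on weekly mean GCSI-DD scores, nausea/vomiting as primary and total as secondary:

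- Include all patients who received an active patch and all observed weeks, with week as a categorical factor and unstructured covariance (six parameters for three levels).
- For the diabetic/idiopathic comparison, add etiology and etiology-by-week.
- State the minimum number of diary days that make a weekly score.
- Ask patients who stop early to keep the diary, where they agree.
- In the responder percentages, count treated patients without an assessment as non-responders.
- As a sensitivity check, set missing week-2 changes to a range of values, from the model's prediction through zero to one SD of change worse than baseline, and report the estimate at each. Use the observed SD of the score being analysed, not the 5 points that belong to the GCSI total. Zero alone is not enough: with no true effect and 20% missing it keeps 80% of the completers' bias.

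The cost is a few sentences of plan wording in software already named, plus voluntary diaries from patients who stop. The estimate may be slightly less favourable. The model removes only part of the bias if dropout depends on the unseen week-2 score (about 0.5 to 0.7 of 0.9 points remains), which is why the sensitivity range is needed.
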